4.4.4 Vital Signs

Descriptive statistics for vital signs parameters (ie, diastolic and systolic BP, pulse, respiration rate, temperature) and weight, and changes from Baseline will be presented by visit and treatment group.

Vital sign values will be listed. Clinically notable vital sign values will be identified on the listings as those above (H) or below (L) a clinically notable range ([Table 1](#)). Categorical analyses of subjects (number and percent) who fall outside the below clinically notable vital sign ranges will also be presented by modal dose group and visit.

Table 1 Vital Sign and Weight

Variable	Criterion value ^a	Change relative to baseline ^a	Clinically notable range
Heart rate	>120 bpm	Increase of ≥ 15 bpm	H
	<50 bpm	Decrease of ≥ 15 bpm	L
Systolic BP	>180 mmHg	Increase of ≥ 20 mmHg	H
	<90 mmHg	Decrease of ≥ 20 mmHg	L
Diastolic BP	>105 mmHg	Increase of ≥ 15 mmHg	H
	<50 mmHg	Decrease of ≥ 15 mmHg	L

BP = blood pressure, bpm = beats per minute, H = high, L = low.

Clinically notable means that a value must meet the criterion value and must attain the specified magnitude of change relative to baseline.

4.4.5 Electrocardiograms

Descriptive statistics for ECG parameters and changes from Baseline will be presented by modal dose group. Shift tables will present changes from Baseline in ECG interpretation (categorized as normal; abnormal, not clinically significant; and abnormal, clinically significant) by visit. Later on, shift tables may be presented by post baseline year instead of visit as deemed appropriate.

For each subject, the maximum observed corrected QT interval calculated using Fridericia's formula (QTcF), and the maximum prolongation from baseline in QTcF will be compiled. Categorical analyses of subjects (number and percent) with maximum observed QTcF values >450 msec, >480 msec, and >500 msec and maximum prolongations (from Baseline) in QTcF >30 msec and >60 msec will be presented by modal dose group and by time point. Categorical analyses of subjects (number and percent) with maximum observed PR values >220 msec, and QRS values > 120 msec will be presented by modal dose group and by visit.

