2.2 Overall Study Design and Plan

2.2.1 Extension Phase

The Extension Phase comprises a 30-month Maintenance Period (Treatment Period) and a 14-day Follow-Up Period.

Subjects who complete the Core Study End of Study (EOS) Visit within 30 days prior to enrollment in the Extension Phase will be eligible for participation.

For subjects continuing directly from the Core Study to the Extension Phase, the End of Study (EOS) Visit of the Core Study will be the start of the Extension Phase.

Subjects who complete the Core Study, but who do not elect to immediately roll over to the Extension Phase will be required to return to the site within 30 days of completion of the Core Study and repeat selected assessments before being dispensed drug for the Extension Phase. If subjects return before 30 days of the last study visit, the tests that are required at that time are vital signs, weight, the Sleep Disorders Inventory (SDI), and the electronic Columbia-Suicide Severity Rating Scale (eC-SSRS). All other data will be carried over from Visit 6A. If subjects return on Day 30, all tests listed for Visit 6B will be performed. Details are as in (Figure 1).

During the Treatment Period, all subjects initially will receive lemborexant 10 mg per day (LEM10). At the discretion of the investigator, subjects will have the option of increasing the dose to lemborexant 15 mg per day (LEM15) or decreasing to lemborexant 5 mg per day (LEM5). All dose adjustments will be performed at an unscheduled visit or at the next scheduled visit.

All doses will be taken orally in tablet form each night for the duration of the Extension Phase immediately (ie, within 5 minutes) before the time the subject intends to sleep. The dose can be adjusted more than once during the Extension Phase. Subjects will receive 1 or 2 tablets as described below:

- LEM5: one lemborexant 5-mg tablet
- LEM10: one lemborexant 10-mg tablet
- LEM15: one lemborexant 5-mg tablet and one lemborexant 10-mg tablet

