4 STATISTICAL METHODS

All descriptive statistics for continuous variables will be reported using mean, standard deviation (SD), median, minimum and maximum. Categorical variables will be summarized as number (percentage) of subjects.

There will be no hypothesis testings, and data will be only be summarized by timepoint and by modal dose received by the subject.

Modal dose will be calculated as follows:

If subject has one dose start date and no dose end date, then subject has been on initial10 mg dose, model dose = 10 mg.

If a subject has start dose date and only one end date, and a second dose start date; then subject has been on 10 mg dose till first end dose date, the number of days on 10 mg is calculated as follows: first end date - first start date +1 , and number of days on the new dose is calculated as: database snapshot date- second start date +1. The modal dose is the most frequent of these two numbers, ... and so on.

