4.3 Efficacy Analyses

SDI will be summarized by visit and modal dose based on the Safety Analysis Set.

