4.4.3 Laboratory Values

Clinical laboratory values will be evaluated for each laboratory parameter by subject for Extension Phase.

Abnormal laboratory values will be identified as those outside (above or below) the normal range. Reference (normal) ranges for laboratory parameters will be included in the clinical study report for this study. Descriptive summary statistics (eg, mean, SD, median, minimum, maximum for continuous variables, and number and percentage for categorical variables) for the laboratory parameters and changes from baseline will be evaluated by modal dose and visit.

Laboratory test results will be assigned a low-normal-high (LNH) classification according to whether the value was below (L), within (N), or above (H) the laboratory parameter's reference range. Within-treatment comparisons will be based on 3 by 3 tables (shift tables) that, for a particular laboratory test, compare the Study Baseline LNH classification to the LNH classification at end of study/early termination, by modal dose.

Clinical laboratory results post-baseline will be evaluated for markedly abnormal values. A laboratory test will be considered markedly abnormal if the result worsens to meet Eisai grading criteria for laboratory values limit of Grade 2 or higher. If the Grade 2 limit is missing, the Grade 1 limit will be considered. [Appendix 12.1](#) presents the Eisai grading criteria for laboratory values that were used to identify subjects with markedly abnormal laboratory values. For the incidence of markedly abnormal laboratory values, each subject may be counted once in the laboratory parameter value high and in the laboratory parameter low categories as applicable.

While this section covers laboratory data starting from Extension Phase baseline, laboratory data before Extension Phase might be presented if deemed appropriate.

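### ECG, laboratory, notable vital-sign and SDI summaries use only a subject-level modal dose, so a value measured on one dose can be counted under another

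*SAP*

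**What the plan says.** Section 2.2.1 (Extension Phase) starts all subjects on LEM10 and lets the investigator move them to LEM15 or LEM5. It adds that "The dose can be adjusted more than once during the Extension Phase" and that "All dose adjustments will be performed at an unscheduled visit or at the next scheduled visit".

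Section 4 sets the general display rule: "data will be only be summarized by timepoint and by modal dose received by the subject". Modal dose comes from counting days on each dose and taking the larger count. For a subject who has switched, the "number of days on the new dose is calculated as: database snapshot date- second start date +1". Each subject therefore has one label, fixed by the whole dosing history to the snapshot.

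The label is then used for dated measurements:

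- ECG (4.4.5): "Descriptive statistics for ECG parameters and changes from Baseline will be presented by modal dose group". The QTcF categories are by modal dose and time point, and the PR and QRS categories by modal dose and visit.
- Laboratory (4.4.3): "the laboratory parameters and changes from baseline will be evaluated by modal dose and visit". Markedly abnormal values fall under the general modal-dose rule of 4.4.
- Vital signs (4.4.4): the clinically notable categories are by modal dose group and visit.
- SDI (4.3): "SDI will be summarized by visit and modal dose based on the Safety Analysis Set".

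Section 4.4 says that safety data, shown by modal dose group, are summarised *as treated*, a term it does not define. Section 4.4.2 adds selected adverse event tables by dose at first onset, within modal dose.

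**The concern.** The objective in section 2.1 is the long-term safety and tolerability of flexible doses of 5, 10 and 15 mg. A reader of a table with LEM5, LEM10 and LEM15 columns will naturally take an abnormality in a column as one that occurred on that dose. Under the modal-dose rule this need not be so, because dosing after the measurement can decide the column.

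The displacement need not be random. Section 4.4.2 foresees adverse events that lead to dose reduction. If an abnormal value on LEM10 is followed by a reduction, and the subject then spends longer on LEM5, the abnormality moves to the lower-dose column. A dose pattern could be masked or reversed.

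Numbers are small. Section 3 gives about 60 subjects for the Core Study, and only eligible completers may enter the Extension, so a few displaced subjects can visibly change a LEM5 or LEM15 percentage.

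The SAP already accepts, for adverse events, that modal dose alone does not show the dose at the event. It makes no such provision for the measured variables.

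**Working it through.** The SAP states no figure to reproduce. The check applies its own modal-dose count to example subjects.

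**From the SAP:** start on LEM10 (2.2.1); treatment up to 30 months (2.2.2); day count to the snapshot (section 4); 30-day visit windows after Visit 7 (7.1.4).

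**Assumed:** 30 windows of 30 days, so T = 30 × 30 = 900 days; no dosing gaps; one assessment in every window, on days 30, 60, …, 900; an assessment on the switch day counted as on the new dose. The SAP gives no switch times. The assessment schedule is in the protocol, and some visits are by telephone (2.2.1), so 30 assessments is a hypothetical number.

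**Formulas, one switch on extension day s:** days on LEM10 = s − 1; days on the new dose = 900 − s + 1 = 901 − s. The label is the new dose if 901 − s > s − 1, that is, s ≤ 450. Day 451 gives a tie (450 against 450), and later switches leave the label at LEM10.

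| Switch day | Days LEM10 | Days new dose | Label | Assessments off the label |
|---|---|---|---|---|
| 15 | 14 | 886 | new | 0 of 30 |
| 45 | 44 | 856 | new | 1 of 30 (3%) |
| 91 | 90 | 810 | new | 3 of 30 (10%) |
| 181 | 180 | 720 | new | 6 of 30 (20%) |
| 361 | 360 | 540 | new | 12 of 30 (40%) |
| 448 | 447 | 453 | new | 14 of 30 (47%) |
| 460 | 459 | 441 | LEM10 | 15 of 30 (50%) |
| 600 | 599 | 301 | LEM10 | 11 of 30 (37%) |

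In the first six rows, LEM10 values are filed under LEM5 or LEM15. In the last two, LEM5 or LEM15 values are filed under LEM10.

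**Three doses:** 300 days on LEM10, then 290 on LEM15, then 310 on LEM5 (total 900) gives the label LEM5. Assessments up to day 590 number 19, so 19 of 30 (63%) are off the label. With three doses the modal dose covers at least one third of the days, so the off-label share of days is at most two thirds.

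**Dependence on the snapshot:** a switch on day 271 gives 270 days on LEM10. At a day-360 snapshot the new dose has 360 − 271 + 1 = 90 days, so the label is LEM10. At day 900 it has 630 days, so the label is the new dose. Section 5 plans interim analyses, so the same early ECG could stand in different columns of two reports.

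**Filed by dose at assessment,** the mismatch is 0 by construction.

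**The case against.** **Modal dose is a legitimate received-dose grouping.** This stands. A reader might infer that section 4.4 contradicts itself by calling such tables *as treated*. The documents do not support that: the term and the modal-dose grouping share one sentence, and nothing defines the term as the dose at the visit. It is a tension left by an undefined term. That sentence also covers safety data only, not the SDI in 4.3.

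**The percentages are constructed.** This also stands. They are bounds for one subject under assumed switch times and a full assessment schedule. Early switching gives 0 or 1 of 30. A reader might infer that the early LEM5 and LEM15 columns hold nothing but LEM10 data. That is not established, because a subject switched at an unscheduled visit before Visit 7 is correctly placed there, and the SAP does not show which assessments occur at Visit 7.

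**Dose-at-assessment columns have their own faults.** Doses are changed at the investigator's discretion, so such columns mix dose with tolerability, response and time on study. Subjects appear more than once, and cells may be small. This is correct, and the proposed tables would not give a clean dose–response comparison. They would, however, state correctly what the subject was taking.

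**The plan is descriptive and the data are not lost.** There is no hypothesis testing, individual data are listed (7.1.3), notable vital signs are flagged in listings (4.4.4), and section 2 permits further exploratory analyses. An outlier can therefore be traced to its dose. This lessens the consequence, but a listing does not replace a planned summary.

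**Conclusion.** The point holds as a gap in presentation that should be closed. The dated ECG, laboratory, notable vital-sign and SDI values are summarised only under a label set by total days on each dose to the snapshot. No planned table of these measurements uses the dose taken when they were made, although selected adverse event tables do use dose at onset.

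The size is unknown from the SAP. Under the stated assumptions, 0 to about 50% of a subject's assessments are off the modal dose with one switch, and 63% in the three-dose example.

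The finding does not show that the modal-dose tables are wrong as a subject-level display. Nor does it show that these measurements are the only dose-related data: section 4.4.1 summarises mean daily and cumulative dose, and section 4.4.2 has the onset-dose tables. The descriptive vital-sign tables are outside the point, since 4.4.4 presents them by treatment group. The ECG descriptive sentence does not itself say by visit; the categorical ECG analyses do name visit or time point.

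**What to change.** Keep the modal-dose tables and make two changes.

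1. Derive the dose being taken at each assessment from the dose start and end dates that section 4 already uses. Add supplementary tables by that dose, at least for the QTcF, PR and QRS outlier categories, markedly abnormal laboratory values and clinically notable vital signs. The denominator is the number of subjects assessed while on that dose. The descriptive summaries and the SDI can be added as an option. Say how an assessment on the day of a dose change, or after the last dose, is assigned.
2. State in 4.4 that modal dose is a subject-level label and not the dose at each visit, and define *as treated* accordingly.

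The cost is one derived variable, extra tables and some SAP text; no new data are needed. Footnotes should say that a subject may appear under more than one dose, that cells may be small, and that the display is descriptive and confounded by titration and time.

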4.2.4 Demographic and Other Baseline Characteristics

Demographic and other baseline characteristics for the Safety Analysis Set will be summarized by modal dose using descriptive statistics. Continuous demographic and baseline variables include age, height, and weight; body mass index (BMI); categorical variables include sex, age group (60 to <65 , 65 to <75 , 75 to <85 , and 85 to 90), BMI group (<18.5 , 18.5 to <25 , 25 to ≤ 30 , and >30 kg/m², or other suitable categorization), race, ethnicity, and country.

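### The PR and QRS outlier counts ignore baseline, so they mix stable pre-existing prolongation with new prolongation in an extension that has no comparator

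*SAP*

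**What the plan says.** SAP section 4.4.5 sets the categorical ECG outputs. For PR and QRS it plans the number and percent of subjects with "maximum observed PR values >220 msec, and QRS values > 120 msec will be presented by modal dose group and by visit". No baseline or change condition is attached, and the sentence does not limit the maximum to ECGs taken after baseline.

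For QTcF the same section gives two kinds of category. One is absolute: "maximum observed QTcF values >450 msec, >480 msec, and >500 msec". The other is relative to baseline: "maximum prolongations (from Baseline) in QTcF >30 msec and >60 msec".

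Two further ECG outputs refer to baseline:
- For the overall reading of the tracing: "Shift tables will present changes from Baseline in ECG interpretation", using three classes (normal; abnormal but not clinically significant; abnormal and clinically significant).
- For the individual measurements: "Descriptive statistics for ECG parameters and changes from Baseline will be presented by modal dose group".

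The neighbouring safety sections build baseline into their outlier rules. Section 4.4.3 calls a post-baseline laboratory result "markedly abnormal if the result worsens to meet Eisai grading criteria". Section 4.4.4 says that, to be clinically notable, "a value must meet the criterion value and must attain the specified magnitude of change relative to baseline".

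**The concern.** An absolute cut-off applied to on-treatment ECGs counts everyone above it, whatever the reason. A long PR or wide QRS that was present at entry and never moves is counted in the same cell as one that appears on lemborexant.

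This matters for three reasons:
- The stated objective is long-term safety and tolerability.
- All subjects start on lemborexant 10 mg and stay on some dose of it. No control column shows the background rate, and the modal-dose columns reflect doses chosen by the investigator, so they are not a randomised comparison.
- There is no hypothesis testing (section 4), so the descriptive counts are themselves the evidence. Section 5 says interim outputs will support new drug applications.

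The age bands in section 4.2.4 run from 60 to 90. Some conduction abnormality at entry is plausible, but the SAP gives no figure for it.

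**Working it through.** The SAP states no figure on this point, so there is nothing to reproduce. The check applies the written rules to individual subjects and then sizes the effect under stated assumptions.

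**Step 1. Apply each rule to a subject who does not change.** The cut-offs are from sections 4.4.4 and 4.4.5; the subjects are hypothetical.

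| Measure | Baseline → later | Rule as written | Counted? |
|---|---|---|---|
| PR | 230 → 230 msec | 230 > 220 | Yes |
| QRS | 130 → 130 msec | 130 > 120 | Yes |
| QTcF, absolute | 455 → 455 msec | 455 > 450 | Yes |
| QTcF, change | 455 → 455 msec | 0 > 30 is false | No |
| Heart rate, low | 48 → 48 bpm | 48 < 50 is met; a fall of at least 15 is not (fall = 0) | No |

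A stable low heart rate is not flagged. A stable QTcF is counted in the absolute category, but the change category shows that it is stable. A stable PR or QRS is counted, and no PR or QRS category shows that it is stable.

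**Step 2. See whether another planned output supplies the missing link.**
- *Change-from-baseline statistics.* Section 4 includes the minimum and maximum, so a large increase would show as the maximum change. It would not show whether that subject is one of those above the limit.
- *Interpretation shift table.* It covers the overall reading. A subject already abnormal but not clinically significant who newly crosses 220 msec can stay in the same cell.
- *By-visit display.* Section 7.1.4 defines Ext. Visit 6B as on or before the first Extension dose, so a baseline count could appear. The SAP does not say that it will. Even if it does, equal counts at baseline and later can hide one resolved case and one new case.
- *Listings (section 7.1.3).* A reader could match each flagged subject to baseline by hand, but this is not a summary.

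**Step 3. Size, for illustration.** The share of subjects above a given limit at baseline is assumed to be 5%, 10% or 20%. Section 3 gives about 60 for Core Study enrolment, used here as an upper bound because only eligible subjects who completed the Core Study after the amendment may enter. The values 40 and 20 show smaller extensions.

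Expected number counted with no drug effect = N × p. Chance of at least one = 1 − (1 − p)^N.

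| N | p = 5% | p = 10% | p = 20% |
|---|---|---|---|
| 60 | 3 (0.954) | 6 (0.998) | 12 (1.000) |
| 40 | 2 (0.871) | 4 (0.985) | 8 (1.000) |
| 20 | 1 (0.642) | 2 (0.878) | 4 (0.988) |

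For example, 60 × 0.05 = 3, and 1 − 0.95^20 = 0.642. In a modal-dose column of 15 subjects (also an assumed size), one such person is 1/15 = 6.7%.

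**Step 4. Test the obvious remedy.** Counting only subjects at or below the limit at baseline brings the stable PR and QRS cases in step 1 to zero. It also loses a subject whose PR goes from 222 to 300 msec: the rise is 300 − 222 = 78 msec, but the baseline is already above 220. The remedy should therefore split the count and not restrict it.

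**The case against.** The strongest reply is that these are plainly described absolute counts in a descriptive plan. Section 4.4.5 does not call them treatment-emergent, as sections 4.4.2 and 4.4.6 do for adverse events and suicidality. Nothing obliges ECG intervals to follow the laboratory or vital-sign rules, so the difference is an asymmetry and not a contradiction. That is correct. A reader might infer that the SAP presents old conduction disease as a drug-emergent abnormality; the text makes no such claim.

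A reader might also extend the point to QTcF, whose >450, >480 and >500 msec categories are equally absolute. The documents do not support this as a defect, because the >30 and >60 msec prolongation categories accompany them and separate stable from new prolongation.

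A third tempting inference is that new PR or QRS cases could not be told from old ones at all. That is too strong. Change statistics with a maximum, interpretation shift tables and subject listings are all planned, and in a small extension the listings can be read through.

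The size is also open to challenge. The prevalence and the column of 15 are assumptions, entry may be well below 60, and eligibility criteria are not in the SAP.

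What survives is narrower: no planned summary table ties a PR or QRS flag to the same subject's baseline, and PR and QRS are the only outlier measures among those compared here with no baseline-referenced category.

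**Conclusion.** The point holds for PR and QRS. As written, their tables report how many subjects are above a limit, with stable and new cases combined, and there is no comparator against which to read the result. That stable cases are counted follows from the wording and needs no assumption. How many subjects are affected cannot be learned from the documents; the 3 to 12 of 60, or 1 to 4 of 20, depend entirely on the assumed 5% to 20%.

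The change is worth making because it alters what the PR and QRS tables can show. It does not make the ECG analysis as a whole invalid, and it does not require any change to QTcF.

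A related gap affects any repair. Section 4.4.5 says only Baseline, while section 4.4.3 uses both a Study Baseline and an Extension Phase baseline, and section 4.4 counts Study Day 1 from the first Core Study dose. An abnormality that first arose during the Core Study would be new under one baseline and pre-existing under the other.

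**What to change.** In section 4.4.5:

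1. Take the PR and QRS maxima over post-baseline ECGs.
2. Keep the absolute counts (PR >220 msec, QRS >120 msec) and split each by baseline status:
   - at or below the limit at baseline and above it afterwards, with subjects at or below the limit at baseline as the denominator;
   - already above the limit at baseline.
3. For subjects already above, also show the change from baseline, so that further worsening is not lost.
4. State whether Baseline means the Core Study or the Extension baseline.
5. Leave the QTcF categories as they are. Adding baseline status to the absolute QTcF table is optional.

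The cost is a few sentences in the SAP, one condition in the ECG program and a few more table rows. No new data are needed, because the planned change statistics already require a baseline ECG. The drawback is that denominators in the split will be small, so numbers of subjects should be shown beside every percentage.
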